Specific Aim 2: Determine the safety of insulin glargine 0.4 unit/kg early administration within four hours from IV Insulin infusion initiation.

III. METHODS

A. Study Design and Methodology:

This will be a prospective, open-label, intervention cohort study including all consecutive adult patients with Diabetes Ketoacidosis (DKA) getting admitted to Fairview Hospital-Medical Intensive Care Unit (FV-MICU). Screening of patient eligibility and informed consent will be done by the MICU admitting physician once the patient gets admitted to MICU. Participants will be given an overview of the study, including study procedures, and potential risks. Participants will be given adequate time to review the consent form and have opportunities to ask questions. After the informed consent process has been completed and a consent form has been signed, a copy of the consent will be provided to the participant and another copy will be secured in the Principle Investigator office in a locked cabinet. Enrolled participants in the intervention group will receive an Insulin Glargine 0.4 Unit/kg within 4 hours from initiating the IV Insulin Infusion, as per the Cleveland Clinic DKA protocol. The remaining of the management will be following the CC DKA protocol including continuing IVII till Anion Gap Closure ($AG \leq 12$), Basal Metabolic Panel Q 2 hrs, and replacing electrolytes as indicated. After closing the anion gap, the decision for giving more Basal Insulin doses will be left to the treating physician's discretion. For patient safety, Point Of Care (POC) blood glucose will be checked hourly before IVII discontinuation. After IVII discontinuation, the BG will be checked with meals, bedtime and 2 am if the patient maintain good oral intake, if not, the BG will be checked q 4 hrs. Target BG 150 – 200 mg/dl during the DKA management and 140 – 180 mg/dl after DKA resolution as per American Diabetes Association recommendations. In case of any hypoglycemia event, this goal will be achieved by using Dextrose containing fluid or carbohydrate enriched oral intake which will be left to the treating physician discretion depending on patient awareness and severity of hypoglycemia. Also, the pre meals and correctional insulin doses after AG closure will be left to the treating physician's discretion. After AG closure the pre meals and correctional insulin doses will be left to the treating physician's discretion. In case of not closing the AG after 24 hours from the initial Glargine dose, the decision for further Glargine doses will be left to the treating physician's discretion.

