
The investigator team will be notified by the MICU attending after each participant enrollment, so one of the team members will present to MICU to collect the data prospectively in a standardized Data Collecting Sheet (DCS) by using REDCap and all protected health information (PHI) will be de-identified. As regards the control group, an E-research request will be submitted to provide a list by

all the consecutive adult patients admitted to FV-MICU with a diagnosis of DKA in the period between January 1st 2019 till the date of IRB approval. Prespecified sample size and matched in basal patient characteristics and DKA severity will be selected as the control group. Data will be collected retrospectively for the control group and will be recorded directly into the DCS in RedCap. Clinical outcomes will be compared between the intervention and control groups. The primary outcome includes time to anion gap closure ($AG \leq 12$). Secondary outcomes include hospital Length Of Stay (LOS), ICU LOS, total IVII dose, the incidence of transitional failure (defined recurrence of DKA after initial IVII discontinuation within 24 hours and requiring reinitiating the IVII), the incidence of hyperglycemia (> 180 mg/dL) and hypoglycemia (defined as ≤ 70 mg/dL, <54 , <40) during 24 hours from Insulin Glargine administration.

B. Definition of main exposures and outcomes:

Diagnosis of DKA will be made by ICD-10-CM code E10.10, E11.10, or meeting the ADA definition; $BG \geq 250$ mg/dl, $AG > 12$, and positive Ketones in serum or urine

DKA classification as the following table from ADA:

	Mild (plasma glucose >250 mg/dl)	Moderate (plasma glucose >250 mg/dl)	Severe (plasma glucose >250 mg/dl)
Arterial pH	7.25–7.30	7.00 to <7.24	<7.00
Serum bicarbonate (mEq/l)	15–18	10 to <15	<10

For the hyperglycemia analysis, patients will be compared in the following categories according to their mean or median (depending on the normality of the data distribution) blood glucose throughout the hospital stay:

- Mean/median BG <80 mg/dL
- Mean/median BG 81-100 mg/dL
- Mean/median BG 101-140 mg/dL
- Mean/median BG 141-180 mg/dL
- Mean/median BG > 180 mg/dL'
- Mean/median BG > 240 mg/dL

Hypoglycemia will be defined by three categories:

- any glucose level below 70 mg/dL
- any glucose level less than 54 mg/dL
- any glucose level less than 40 mg/dL

For Time of Anion Gap Closure (TAGC) will use the ADA definition: $AG \leq 12$ mEq/L

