- Non-insulin antihyperglycemics taken at home prior to admission, including the type
 - Sulfonylureas
 - Thiazolidinediones
 - Dipeptidyl peptidase-4 (DPP-4) inhibitors
 - Biguanides
 - Glucagon like peptide-1 (GLP-1) analogues
 - Sodium-glucose transport protein 2 (SGLT2) inhibitors
 - Meglitinides
 - Alpha glucosidase inhibitors
 - Amylin analogues
- History of immunosuppression (history of cancer, HIV or auto-immune disease or organ transplant, chronic steroid)

Initial Laboratory values:

- Anion gap (mEq/L)
- Bicarbonate (mEq/L)
- Glucose (mg/dL)
- Beta-Hydroxybutyrate (mmol/L)
- Ketones in the urine (Y/N/Unknown)
- HbA1c %
- Lactate (mmol/L)

Intervention and outcomes:

- IV insulin infusion starting time
- Insulin glargine administration time
- Anion Gap closure time
- IV insulin discontinuation time
- Number of hours of IVII
- Total IV insulin infusion has been given
- Total IV insulin/weight
- Total IV fluid during DKA management
- Date of discharge from ICU
- Date of discharge from hospital
- Hospital Length Of Stay (days)
- ICU LOS (hours)
- Transitional failure (recurrence of DKA)?

Hypoglycemia Events

- Hypoglycemia event within 24 hrs from glargine
- Time of the hypoglycemia
- How many hours after the glargine administration?
- Severity
- How it has been treated

Hyperglycemia Events

- Hyperglycemia Event after IVII discontinuation by 24 hours (Y/N)
- time of the hyperglycemia event
- Severity of hyperglycemia
- How many hours after IVII discontinuation

D. Outcomes

Primary outcome: Time to anion gap closure (hours).

Secondary outcomes:

- Hospital Length of stay (days)
- ICU length of stay (hours)
- Total IV insulin infusion dose (International unit)
- Incidence of transitional failure (percentage).
- Incidence of hyperglycemia (> 180 mg/dL) during 24 hours from Insulin Glargine administration (percentage).
- Incidence of hypoglycemia (defined as ≤ 70 mg/dL, <54, <40) during 24 hours from Insulin Glargine administration (percentage).

IV. DATA COLLECTION

For the control group, the data will be collected retrospectively and recorded in standardized DCS in RedCap. For the intervention group, the data will be collected prospectively by the investigator team members and observations will be recorded in standardized DCS in RedCap. All protected health information (PHI) will be de-identified for both intervention and control group by using de-identification function in REDCap.

V. DATA ANALYSIS

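### Hypoglycemia is counted for only 24 h from glargine, although further basal insulin is allowed from anion gap closure onward and those later doses are not among the listed variables

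*Combined protocol and SAP*

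**What the plan says.** - **Window.** The III.C list of hypoglycemia variables opens with "Hypoglycemia event within 24 hrs from glargine". The secondary outcome in III.D is an incidence "during 24 hours from Insulin Glargine administration (percentage)", and III.A uses the same period.
- **Further basal insulin.** III.A says: "After closing the anion gap, the decision for giving more Basal Insulin doses will be left to the treating physician's discretion". For a gap that stays open it adds: "In case of not closing the AG after 24 hours from the initial Glargine dose, the decision for further Glargine doses" are also for the physician to decide. No interval from the first dose is stated.
- **What is recorded.** Under Intervention and outcomes, III.C lists "Insulin glargine administration time" once. It lists no units for that dose and no time or units for any later basal dose.
- **Definition.** III.B defines three tiers, the first being "any glucose level below 70 mg/dL", with no time limit. It also groups patients by mean or median glucose over the whole stay, but that is a summary of level and not a count of low values.
- **Other outcomes.** The III.C hyperglycemia field, and transitional failure as defined in III.A and III.B, are timed to 24 h after the infusion stops. The hyperglycemia outcome in III.D, by contrast, is timed from glargine.

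**The concern.** Specific Aim 2 is to determine the safety of the early 0.4 unit/kg dose, and hypoglycemia is the treatment risk that Section VIII names. Section VIII explains the lack of excess hypoglycemia in earlier studies by hourly adjustment of the infusion. That mechanism ends when the infusion stops, and glucose checks then become less frequent (mealtimes, bedtime and one overnight check, or four-hourly). This is also when further basal insulin may be given to a patient who has already had the study dose.

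Followed as written, the trial could report no excess hypoglycemia while low values after hour 24 are not counted as events. Because later basal doses are not listed for collection, the report also could not say whether physicians gave or withheld them. Meanwhile, rebound hyperglycemia and recurrence of DKA are sought in the same charts over later hours.

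**Working it through.** **Inputs.** Section V gives a mean time to closure of 15.6 h, SD 6 h, an expected 20% difference, one-sided alpha 0.025, beta 0.10 and 160 patients in total. Section III gives glargine 0-4 h after infusion start and the 24 h window.

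**Assumptions.** The closure clock starts with the infusion, allocation is 1:1, and the 24 h run from the first glargine dose. The documents state none of these outright.

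**The plan's own figure.** The difference is 0.20 × 15.6 = 3.12 h. The per-group size is 2 × (1.960 + 1.282)² × 6² / 3.12² = 77.7, so 78 per group and 156 in total (158 with the t distribution). This agrees with the stated 160, so the inputs are being read as the plan uses them.

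**Time from glargine to closure.** Expected closure in the intervention group is 15.6 × 0.8 = 12.48 h after infusion start. Subtracting the 0-4 h delay gives s = 8.48 to 12.48 h after glargine.

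**Share of the 24 h after a further dose that is uncounted.** A further dose given s hours after the first has 24 − s hours left in the window, so the uncounted share of its next 24 h is s/24, up to a maximum of 1.

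| Further dose given | s (h after first dose) | Hours counted | Uncounted share of next 24 h |
|---|---|---|---|
| At closure, 20% benefit (12.48 h) | 8.48-12.48 | 15.5-11.5 | 35-52% |
| At closure, no benefit (15.6 h) | 11.6-15.6 | 12.4-8.4 | 48-65% |
| 24 h or more after the first | ≥24 | 0 | 100% |

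Averaging by simulation over closure times (SD 6 h; normal, gamma or lognormal) and a delay uniform on 0-4 h gives a mean uncounted share of 43-46% with the expected benefit and 55-57% without it.

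**Gap still open 24 h after glargine.** This needs closure later than 24 to 28 h after infusion start. For a normal distribution with mean 12.48 and SD 6, z = (24 − 12.48)/6 = 1.92 gives 2.7%, and z = (28 − 12.48)/6 = 2.59 gives 0.5%. With 80 patients that is 2.2 to 0.4, so about 0-2 patients. The skewed distributions above, averaged over the delay, give about 3%.

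**Two-dose overlap.** This needs a duration of action D, which the documents do not give. If both doses act for D hours, the uncounted share of the overlap is max(0, D − 24)/(D − s). For s = 8.48-12.48 h it is:
- D of 24 h or less: 0%
- D = 30 h: 6/21.52 to 6/17.52 = 28-34%
- D = 36 h: 12/27.52 to 12/23.52 = 44-51%

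**Comparison with the other follow-up.** If the infusion stops at expected closure, the hyperglycemia field and transitional failure run to 8.48 + 24 = 32.5 h up to 12.48 + 24 = 36.5 h after glargine, against 24 h for hypoglycemia.

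**The case against.** Aim 2 concerns the early dose, and a 24 h count from that dose is a defensible match to it. Later events increasingly reflect the physician's own dosing. The overlap that Section VIII discusses is glargine with the infusion, and at expected closure that period lies inside the window. The III.B definition is untimed, the whole-stay glucose analysis needs later values in any case, and the phrase about glargine could be read as applying to each dose. How many patients get a further dose, and when, is unknown.

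Much of this stands, and it limits what can be claimed. Three stronger readings are tempting, and the documents do not support them:
- A reader might infer that most of the period with two doses acting together is missed. With an assumed action of 24 h or less, none of it is. The 35-52% is a share of the 24 h after the further dose, which is a different quantity.
- A reader might infer that overlap with later basal insulin is the main hazard. The documents do not say so.
- A reader might infer that no event can be attributed. Closure time and event time are both listed, and further doses are permitted only after closure or, with an open gap, after 24 h. Under the plan, an in-window event before closure therefore precedes any further dose. Only events after closure are ambiguous.

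The planned first dose can also be derived from recorded weight, so only departures from it are lost. The data collection sheet itself is an appendix whose contents are not in the text, so the remark about missing fields rests on the III.C list.

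The objection does not close the gap. Untimed thresholds and whole-stay averages do not make a low value at hour 30 a counted event, and the single glargine time field favours the first-dose reading.

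**Conclusion.** The point holds in limited form. The counted window ends before much of the follow-up that would apply to further basal doses the plan itself permits, and those doses are not listed for collection. For a further dose given at expected closure, about 35-52% of its next 24 h is uncounted (48-65% if closure is no faster than in the Section V figures). For a dose given 24 h or more after the first, all of it is uncounted. The open-gap route to such a dose is rare; the larger group is likely to be those given more basal insulin at or after closure, for which the documents give no figure.

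The result rests on the closure clock starting with the infusion, on the window running from the first dose, and on further doses actually being given. The missed share of true two-dose overlap is unknown and could be zero. The hours after the infusion stops are already followed for hyperglycemia and transitional failure, so the shorter follow-up for hypoglycemia is hard to justify. The plan should be changed here, though the primary analysis and the sample size are unaffected.

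**What to change.** 1. Keep the 24 h hypoglycemia count and state that it runs from the first glargine dose. Its comparability with controls, who by III.C had no basal insulin before closure, is a separate question.
2. Also collect and report all three tiers over a longer fixed period: for example to 48 h after the first glargine dose, or at least to 24 h after the infusion stops, to match the hyperglycemia field.
3. Record the actual first glargine dose in units, and the time and units of each later basal dose in that period.
4. Report events after closure by whether a further basal dose had already been given. This is descriptive, since physicians choose who receives one.
5. Reconcile the untimed III.B definition with the outcome window.

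The cost is a few added fields and modest extra chart abstraction. Glucose checks after the infusion are already scheduled, and one trial cited in the background reports mean stays of 5.1 and 5.9 days. A full log of pre-meal and correctional insulin would be a much larger task and is not asked for, so events due to those doses will remain hard to separate.

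There are limits. Later events partly reflect discretionary dosing. Patients discharged before the longer period ends are incompletely observed, and because length of stay is itself an outcome, their number must be reported by group. A 48 h window still gives less than 24 h of follow-up to doses given later than 24 h after the first. No change to who receives further insulin, or when, is proposed.

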Early administration of basal insulin has seldom been studied in DKA management. In 2012, Hsia et al (4) conducted a prospective randomized controlled trial involving 61 hospitalized adults with known diabetes and presented by hyperglycemia who were randomized to receive treatment with IV insulin infusion (IVII) with or without glargine (0.25 Unit/kg). The primary outcome of rebound hyperglycemia was reduced with early administration of glargine (33.3% vs 93.5%, $P < 0.001$) without increasing the risk of hypoglycemia (none in the intervention group vs three cases in the control group). Accordingly, in 2013, the Joint British Diabetes Societies updated their guideline on DKA management in adults to advise early administration of home basal insulin dose (5). After that, two randomized controlled trials were published in 2015, both with a sample size of 40 patients, investigated initiating Insulin Glargine within 2-3 hrs from IVII initiation compared to IVII alone, using a dose of 0.3 unit/kg (6) and 0.4 unit/kg (7). Although both the studies did not demonstrate statistical significance in the primary and secondary outcomes, it could be argued they were clinically significant. For examples, time to AG closure 13 +/- 6 vs 16 +/- 6 hours, IVII dosage 84 ±45 U vs 116 ± 91 U, rebound hyperglycemia for 24 hours after DKA resolution 35% vs 51%, hospital LOS 5.1 vs 5.9 days (intervention and control groups respectively) (7) and no difference in hypoglycemia events between both groups in both studies.

The limitations in the previous studies such as being underpowered, flaws in reporting data, and lacking a unified management protocol make it difficult to state a definitive evidence-based recommendation for using basal insulin early in DKA in adults. For that reason, we propose prospective, open-label, intervention cohort study to test our hypothesis that an insulin glargine dose of 0.4 Units/kg early administered (within four hours) of IVII initiation in DKA management in adult would be effective and safe in shortening the time to anion gap closure comparing to the standard practice.

II. STUDY OBJECTIVE(S): INCLUDING SPECIFIC AIMS AND/OR HYPOTHESES

Specific Aim 1: Test the hypothesis that early Glargine 0.4 unit/kg administration within 4 hours from IV insulin initiation will provide faster anion gap closure in Diabetic Ketoacidosis management in MICU, at least 20% than late administration.

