Transitional failure will be defined as the recurrence of DKA ($BG \geq 250$ mg/dl, $AG > 12$, and positive Ketones in serum or urine) after initial IVII discontinuation within 24 hours and requiring reinitiating the IVII.

C. Study Population

Intervention vs Control group

- Intervention group: All consecutive adult patients getting admitted to FV- MICU and meet the inclusion criteria and accepted to receive insulin glargine early as per the protocol. They will receive insulin glargine 0.4 unit/kg within 4 hours from initiating the IV Insulin Infusion, as per the Cleveland Clinic DKA protocol.
- Control group: prespecified and matched sample size, consecutive adults who admitted to FV-MICU with a diagnosis of DKA in the period between January 1st 2019 till the IRB approval date and didn't receive basal insulin before AG closure.

Inclusion criteria:

- Age \geq 18 years old
- Meet DKA definition as above
- Having the capacity to sign Informed consent

Exclusion Criteria

- IV insulin infusion initiated more than 4 hours.
- Persistent hypotension (SBP<80 mmHg despite receiving 1000cc normal saline).
- Require Vasopressor
- Acute Coronary Syndrome
- Pregnant
- End-stage renal disease
- Unwilling to consent to participate in the trial
- Currently under police custody
- Transferred from another hospital
- Require emergent surgery
- Alcoholic Ketoacidosis

Study Variables:

General Informations:

- Patient name
- MRN
- Age
- Sex (Male, Female, Others)
- Race (White, Black, Asian, Other)
- Ethnicity (Hispanic vs. Non-Hispanic)
- Weight on admission (kg)
- BMI (Kg/m²)
- Height (cm)
- Date of Hospital admission
- Date of ICU admission

- Date of DKA diagnosis (MM/DD/YY)
- Precipitating cause of DKA
 - Noncompliance
 - New-onset
 - Infection
 - Cerebrovascular accident
 - alcohol abuse
 - pancreatitis
 - Drugs
 - Others

Past Medical history

- Type of diabetes:
 - Type 1 DM
 - Type 2 DM
 - Cystic fibrosis-related diabetes
 - Steroid-induced diabetes
 - Other or no clear diagnosis
- Known diagnosis of other major medical comorbidities (CAD, CHF, HTN, COPD, asthma, liver disease, CKD, cancer, other)
- On Renal Replacement Therapy (Y/N)
- Using Basal insulin at home (Yes/No/ unknown)
- If previous point answer is yes check the corresponding insulin type and write the dose: (Glargine, Detemir, Degludec, NPH, Continuous Insulin Pump) (dose: IU)
- Home total basal insulin dose (units)

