The sample size calculation considered the average time of AG closure in the last 3 months in FV-MICU was 15.6 ± 2.5 hours (CI 95%) and SD of 6 hours. Using one-sided α of 0.025 and an β of 0.10, an expected 20% difference between the two groups, a sample size of 160 totally of the participant will be adequate.

Categorical variables will be described as frequency rates and percentages, and continuous variables will be described using mean, median, and interquartile range (IQR). Proportions for categorical variables will be compared by Chi-squared test of Fisher's exact test. Means for continuous variables will be compared by Student's t-test if normally distributed and Mann-Whitney test if not normally distributed. All statistical analyses will be performed with a one-sided p-value < 0.025 to determine statistical significance. All statistical analyses will be completed by study investigators using Statistical Analysis Software (SAS).

VI. DATA AND SAFETY MONITORING PLAN (if applicable)

All data will be stored in a secured REDcap database. No PHI will be saved on non-HIPAA protected devices. All protected health information (PHI) will be de-identified by using RedCap.

To ensure patient safety, CCF Hypoglycemia protocol is getting followed in all patients receiving insulin including our enrolled participants. Before IV insulin discontinuation, the blood glucose level is getting checked hourly as per protocol. Once the AG is closed and insulin infusion is discontinued, the patient who is maintaining oral intake, blood glucose will be checked with meals, bedtime, and 2 am. If the patient having poor oral intake, blood glucose will be checked q 4 hours. Different treatment options for any hypoglycemic events are available in the protocol depending on the severity of the hypoglycemia event and patient awareness, ranging from oral carbohydrate supplement to IV fluid containing dextrose.

VII. STUDY LIMITATIONS

- Retrospective EPIC data review for the control group. Single-center.

VIII. ETHICAL CONSIDERATIONS

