For patient safety, insulin therapy is carrying a risk of hypoglycemia events. Previous studies didn't show any additional risk when insulin glargine has been given before anion gap closure comparing to the common practice, after anion gap closure. Shankar and Hsia's studies (4, 8) didn't reveal any hypoglycemic events between both groups. Both Doshi and Houshyar's studies (6, 7) revealed similar hypoglycemic events between both intervention and control groups and were neither clinically nor statistically significant.

The possible explanation for that is although the overlap time of glargine and IV insulin infusion is longer in the intervention group, the insulin infusion rate is getting adjusted hourly to meet the body requirement to decrease the blood sugar by a range of 50 - 100 mg/dl per hour. To ensure patient safety, CCF Hypoglycemia protocol is getting followed in all patients receiving insulin including our enrolled participants. Before IV insulin discontinuation, the blood glucose level is getting checked hourly as per protocol. Once the AG is closed and insulin infusion is discontinued, the patient who is maintaining oral intake, blood glucose will be checked with meals, bedtime, and 2 am. If the patient having poor oral intake, blood glucose will be checked q 4 hours. Different treatment options for any hypoglycemic events are available in the protocol depending on the severity of the hypoglycemia event and patient awareness, ranging from oral carbohydrate supplement to IV fluid containing dextrose. After AG closure the pre meals and correctional insulin doses will be left to the treating physician's discretion.

For data safety, all data will remain anonymous, and no personal health information will be associated with any data resulting from this study. Data will recorded directly into a secure REDCap database. No PHI will be saved on non-HIPAA protected devices. All protected health information (PHI) will be de-identified by using RedCap.

All subjects will be provided a consent form describing this study and with sufficient information to make an informed decision about participation in the study. The consent form will be submitted with the protocol for review and approval by the IRB. The formal consent of a subject, using the IRB-

approved consent form, will be obtained before the subject undergoes any study procedure. This consent form must be signed by the subject, and the investigator-designated research staff obtaining the consent.

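### Total IV insulin is compared in raw units with no allowance for body weight between non-randomized groups, although weight and dose per kg are already collected

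*Combined protocol and SAP*

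**What the plan says.** Section III.D lists the secondary outcome as "Total IV insulin infusion dose (International unit", which is not scaled to body size. The study variables in section III.C include "Weight on admission (kg" and, under the intervention and outcome items, "Total IV insulin/weight". The scaled version is not in the outcome list.

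The design (section III.A) is a "prospective, open-label, intervention cohort study including all consecutive adult patients", set against retrospective controls admitted to the same unit from January 2019 onward. Section III.A also says that a sample "matched in basal patient characteristics and DKA severity will be selected as the control group". No matching variables, calipers or method are named.

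Section V gives the analysis: "Means for continuous variables will be compared by Student's t-test if normally distributed and Mann-Whitney test if not normally distributed". No covariate adjustment or matched analysis is described. On how the infusion is run, section VIII says that "the insulin infusion rate is getting adjusted hourly to meet the body requirement".

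The only IV insulin benchmark is in the background, before section II, from one of the two earlier 40-patient trials: "IVII dosage 84 ±45 U vs 116 ± 91 U" (early glargine against control).

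**The concern.** With no randomization, nothing in the design ensures that the groups have the same mean weight. If heavier patients need more IV insulin, a systematic weight difference feeds straight into total units, and the planned test cannot tell it from a treatment effect. Between-patient variation in weight would also widen the spread of raw units and cost some power. The plan collects both quantities needed to deal with this but does not say how they will be used. That also leaves the choice between two versions of the same outcome open until the data are in.

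**Working it through.** **Inputs from the documents.** Cited IV insulin dose: 84 U (SD 45) with early glargine, 116 U (SD 91) in control, difference 32 U. Total sample 160, one-sided alpha 0.025. Primary outcome: mean 15.6 h, SD 6 h, 20% difference, beta 0.10.

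**Inputs assumed.** 1:1 allocation (80 per group; the ratio is not stated). Weight CV 0.15 to 0.30. Treated group lighter by 5% to 15%. Weight independent of the remaining variation in dose. All power figures use the normal approximation.

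**Step 1: the plan's own figure.** The primary difference is 0.20 × 15.6 = 3.12 h. Per group, n = 2 × (1.960 + 1.282)² × 6² / 3.12² = 77.7, so 78, or 156 in total. The t-based version gives 79 per group, 158 in total. The stated 160 reproduces. It concerns the primary outcome only; the plan gives no power figure for IV insulin.

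**Step 2: power for IV insulin in raw units.** SE = √((45² + 91²)/80) = √(10306/80) = 11.35 U. Then 32/11.35 − 1.960 = 0.86, which gives power of 80.5%.

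**Step 3: false saving if dose is proportional to weight.** With no treatment effect and a control mean of 116 U, the shift is 116 × the relative weight difference. The last column is the chance of a false positive when the dose CV is 91/116 = 0.78 (lower figure) or 45/84 = 0.54 (higher figure).

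| Treated group lighter by | False saving | Share of 32 U | One-sided type I error (nominal 2.5%) |
|---|---|---|---|
| 5% | 5.8 U | 18% | 6.1-8.8% |
| 10% | 11.6 U | 36% | 13.3-23.6% |
| 15% | 17.4 U | 54% | 25.6-47.9% |

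Example, 10% and CV 0.78: the SDs are 91 and 0.9 × 91 = 81.9, so SE = √((91² + 81.9²)/80) = 13.69. Then 11.6/13.69 − 1.960 = −1.11, which gives 13.3%.

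**Step 4: power of dose per kg in two opposite cases.**
- Dose proportional to weight: 1 + CV_raw² = (1 + CV_perkg²)(1 + CV_weight²).
- Dose independent of weight: 1 + CV_perkg² = (1 + CV_raw²)(1 + CV_weight²).

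| Weight CV | Power per kg, dose proportional | Power per kg, dose independent |
|---|---|---|
| 0.15 | 83.1% | 77.9% |
| 0.20 | 85.0% | 75.9% |
| 0.25 | 87.4% | 73.5% |
| 0.30 | 90.1% | 70.6% |

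Example, weight CV 0.30, proportional: the per-kg CVs are √(1.287/1.09 − 1) = 0.425 and √(1.615/1.09 − 1) = 0.694. On the scale of the cited means the SDs are 35.7 and 80.5, so SE = √((35.7² + 80.5²)/80) = 9.85. Then 32/9.85 − 1.960 = 1.29, which gives 90.1%. In the proportional case the two-arm variance falls by about 7% at weight CV 0.15 and 25% at 0.30.

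**Step 5: between the two cases.** If dose varies as weight to the power b, the weight-related part of the log dose is proportional to b in raw units and to b − 1 per kg. Dividing by weight therefore helps when b is above 0.5 and harms when it is below.

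**The case against.** The strongest objection is to the premise. A reader might infer, from glargine being given per kg, that IV insulin is also dosed by weight and that raw units therefore must add noise. The documents do not support that. Glargine is a different, single weight-based dose, while section VIII describes an infusion rate adjusted hourly. The institutional DKA protocol is cited but not reproduced. The loss of precision from raw units is therefore conditional, and Step 4 shows that it can reverse. The bias can reverse too: if dose does not depend on weight and the treated group is 10% lighter, dividing by weight makes its dose look about 11% higher (1/0.9 = 1.11). This objection stands, and it rules out simply replacing raw units by units per kg.

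Second, a reader might infer that the plan does nothing about group differences. It does promise matching on baseline characteristics, and weight, height and BMI are all collected. That would limit the problem if weight or BMI were matched, but the text does not say so.

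Third, per-kg dose is not plainly unused. It sits among the intervention and outcome variables, and the general rule for continuous variables in section V could be read to cover it. What can be said is that it is not a listed outcome and has no stated role.

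Fourth, large imbalances need a systematic cause. With 80 per group and weight CV 0.20 to 0.30, the standard error of the relative weight difference is CV × √(2/80), or 3.2% to 4.7%. A 10% gap is thus 2.1 to 3.2 standard errors, and both groups come from the same unit. Differences in calendar period and consent could produce such a shift, but the documents give no evidence of one. Also, 116 ± 91 U suggests skew, so the rank test may be used, and the power figures carry over to it only approximately.

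**Conclusion.** The point holds as a minor one. The documents establish a raw-unit outcome, non-randomized groups, an unadjusted test, matching variables left unnamed, and weight data collected with no stated use. Together these leave open a route by which a weight difference could look like an insulin-sparing effect. Its size depends on two things that the documents do not give: how strongly dose follows weight, and how far the groups differ. Under proportionality, a 5% to 15% difference gives a false saving of about 6 to 17 U against the cited 32 U.

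The precision argument is weaker. Per-kg dose would raise power from about 80% to 83-90% under proportionality and lower it to about 71-78% if dose does not depend on weight. The documents do not support a reading that the raw-unit comparison is certainly biased, or that units per kg is certainly the better outcome. Neither the primary outcome nor the sample size of 160 is touched.

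**What to change.** Three changes of wording, in sections III.A, III.D and V:

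- Prespecify the comparison of total IV insulin as raw units with admission weight as a covariate, on the log scale if the distribution is skewed. The data then estimate how dose depends on weight, and proportionality is not forced.
- Name units per kg as a companion outcome reported beside raw units. This keeps the link to the cited 84 and 116 U and settles before the data are seen which version carries the test.
- State that weight or BMI is among the matching variables.

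The cost is slightly more analysis work. Weight and dose per kg are already on the data list, and the sample size does not change. Adjusting for weight deals with weight only; other differences between treated patients and historical controls remain.
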